7.2 Dealing with Serious Adverse Events

7.2.1 Definition of Serious Adverse Event

Serious adverse events refer to the following adverse events occurring at any dose of the test drug or at any time during the observation period, including the need for hospitalization, prolonged hospitalization time, disability, impairment of working ability, life-threatening or death-threatening events.

7.2.2 Treatment and Report of Serious Adverse Events

If serious adverse events occur in the trial, the unit undertaking the clinical trial shall take necessary measures immediately to protect the safety of the subjects, and report to the local provincial drug supervision and administration department, the State Food and Drug Administration, the applicant and the ethical committee of the

unit responsible for the clinical trial within 24 hours, and notify the experimental units. The applicant will ensure that the reporting procedure meets all legal and regulatory requirements.

Table 7.2.2 Contacts for reporting serious adverse events

Organization	Contacts	Telephone	Fax
Ethics Committee of Xiyuan Hospital, Chinese Academy of Traditional Chinese Medicine	[name]	[name]	[name]
Guizhou Jingcheng Pharmaceutical Co., Ltd.	[name]	[name]	[name]
Beijing Duheng for Drug Evaluation and Research Co., Ltd. (DDER)	[name]	[name]	[name]
CFDA Drug and Cosmetics Registration and Administration Department, Drug Research and Supervision Department	-----	[name]	[name]

7.2.3 Recording of serious adverse events

Researchers must fill in the "Serious Adverse Events Report Form", record the occurrence time, duration, measures taken and outcome of serious adverse events, and sign and date the report.

7.3 Disassembly and Processing of Emergency Letters

Emergency letters are called emergency blindness cracking only when the subject has serious adverse events and needs to identify the types of drugs used immediately. Once blindness is broken, the subject will be discontinued and treated as an exfoliated case. At the same time, the results will be notified to the unit responsible for the test, the bidder and the inspector. Researchers should record the reasons for breaking the blindness, date it and sign it in the case report form.

7.4 Follow-up of unremitted adverse events

All adverse events that have not been completely alleviated at the end of the course of treatment should be tracked and observed to be properly resolved or stable.

8. Evaluation of clinical trials

8.1 Evaluation of clinical effectiveness

Referring to the Guiding Principles of Clinical Research Technology of Traditional Chinese Medicine and Natural Medicine for Coronary Heart Disease and Angina Pectoris.

8.1.2 Evaluation criteria of secondary efficacy indicators

1) The curative effect of TCM syndrome scoring:

Relevant statistical methods were used to analyze the score reduction value and 50% score reduction rate of the two groups.

2) Grading changes of severity of angina pectoris: Comparing the severity grading of CCS angina pectoris between the two groups before and after treatment, and evaluating the therapeutic effect of drugs on chronic stable angina pectoris.

3) The change of angina pectoris attack times per week: The change of angina pectoris attack times per week before and after treatment was compared between the two groups.

4) Nitroglycerin consumption: The corresponding statistical methods were used to analyze the consumption of nitroglycerin before and after treatment in the two groups.

5)SAQ: Compare the changes of each dimension of the Seattle Angina Scale before and after the treatment of the two groups, and evaluate the effects of drugs on the body function and quality of life of the subjects.

6) Change of HCY: Compare the changes of HCY before and after treatment in the two groups, and evaluate the effect of drugs on reducing the incidence of heart disease.

7) Incidence of cardiovascular events (sudden cardiac death, acute myocardial infarction, heart failure, percutaneous transluminal coronary angioplasty, coronary artery bypass grafting, malignant arrhythmia, cardiogenic cerebrovascular accident, angina pectoris requiring hospitalization, etc.).心血管事件发生率(心源性猝死、急性心肌梗死、心力衰竭、经皮冠状动脉腔内血管成形术、冠状动脉搭桥术、恶性心律失常、心源性脑血管意外、需要住院治疗的心绞痛等)。

8.2 Clinical safety evaluation

1. Possible adverse reaction symptoms.

2. General physical examination items, such as body temperature, pulse, breathing, blood pressure, etc.

3. Laboratory examination: blood routine, urine routine, stool routine + Occult blood, electrocardiogram, liver function (ALT, AST, ALP, GGT, TBIL), renal function (BUN, Cr), coagulation, fasting blood sugar, blood lipid.

9. data management

(1) Fill-in and transfer of case report form (CRF)

The completed case report forms are reviewed by clinical researchers and monitors, and then submitted to the data statistical units for data entry and management. All processes need to be documented.

(2) Data input and modification

Data entry and management reasons are the responsibility of data managers in statistical units. Two data managers independently enter and proofread two copies. Questions on the case report form. Data managers will fill in the Question Answer Form (DRO) and send inquiries to researchers through clinical monitors. Researchers should answer and return the questions as soon as possible. Data managers modify the data according to the researchers' answers, confirm and input them, and then issue DRO again if necessary.

(3) Locking of database

After blindly checking and confirming the correctness of the database, the main researchers, bidders and statisticians lock the database. If the problem is found after database locking, it can be corrected in the process of statistical analysis after confirmation, and recorded and explained.

(4) blindness elimination

After all the research data are checked and locked, the first blindness detection is carried out, and then the statistical analysis is carried out according to the statistical plan, the statistical analysis report is written, and finally the second blindness detection is carried out.

10. statistical analysis

10.1 Analytical Data Set

(1) Full Analysis Set (FAS): refers to the ideal set of subjects as close as possible to the principle of intentional analysis. The data set is derived from all randomized participants by eliminating the participants with the least and reasonable method.

(2) PPS: It is a subset of the total analysis set. These subjects are more compliant with the scheme. Compliance includes the following considerations, such as the treatment they received, the absence of major efficacy indicators, and the absence of major violations of the research scheme.

(3) Safety Data Set (SS): When evaluating safety and tolerance, the set of subjects used to aggregate is called Safety Data Set. Subjects who received at least one treatment after randomization were included in the safety analysis set.

10.2 Statistical analysis method

10.2.1 Statistical description

(1) whether it conforms to normal distribution: modifying statistical methods or transforming data when it does not conform;

(2) Whether there is outlier value or not: make statistical and professional analysis to decide whether to choose or not;

(3) Processing the missing value of the main therapeutic index data: When the main therapeutic effect data of individual subjects are missing, the way to fill the missing data is determined from the statistical and professional point of view. For missing cases, the data were transferred from the previous measurements; for missing data, the measurements were made only once, and the mean of all the data was used to fill in the missing data.

(4) The proportion of exfoliated cases: generally not more than 20%, otherwise it should be analyzed and explained;

(5) Descriptive statistical analysis: calculating mean, standard deviation, confidence interval, maximum, minimum, median, frequency (constituent ratio), etc.

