4.8 Exfoliation excluded cases

4.8.1 The withdrawal of the researcher's decision

Subject withdrawal from the study refers to the decision to withdraw the case from the study according to the judgement of the researcher when the selected subjects are unsuitable for further study in the course of the study.

① In the study, patients with aggravated or aggravated conditions, such as increased number of angina attacks, prolonged duration of each attack or aggravated pain, must take emergency treatment measures such as adjusting treatment drugs, hospitalization or surgery;

② In the study, some complications, complications or special physiological changes occurred in the subjects, and it was not appropriate to continue the study;

③ Prohibited drugs prescribed by the scheme were used in the study。

④ In the study, if angina symptoms worsened in the subjects, those who were judged by the researchers to need to take other angina medicines or increase the dosage of drugs were withdrawn as invalid cases。

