4.8.2 Subjects withdraw spontaneously

According to the informed consent, the subjects have the right to withdraw from the study halfway, or they have not explicitly proposed to withdraw from the study, but no longer accept medication and testing and lost interviews, which also belongs to "withdrawal" (or "fall off"). The reasons for their withdrawal should be understood and recorded as far as possible. Such as: poor self-efficacy; intolerable to some adverse reactions; unable to continue to accept clinical research; economic factors; or missing interviews without explaining the reasons.

Whatever the reason, the case records should be kept for the withdrawal cases, and the final test results should be transferred to the final results. The efficacy and adverse reactions of the withdrawal cases should be analyzed by a full data set. All withdrawal cases should be filled in the case report form, the conclusion form and the reasons for withdrawal. In general, there are six kinds, namely, adverse events

(including adverse drug reactions and allergic reactions), lack of efficacy (deterioration or complications), violation of research programs, loss of interviews (including withdrawal of the subjects themselves), suspension of the applicant and others.

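### For a subject who improves and then withdraws for worsening angina, the protocol supports two primary outcomes in the FAS (carried-forward *effective*, or *invalid*) and states no precedence

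*Protocol*

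**What the plan says.** **Carry-forward.** Section 10.2.1(3) covers missing primary data: "For missing cases, the data were transferred from the previous measurements". It makes no exception for withdrawal because of worsening. It also says that "the way to fill the missing data is determined from the statistical and professional point of view", without saying when. Section 4.8.2 states that, regardless of the cause of leaving, "the final test results should be transferred to the final results", and adds: "The efficacy and adverse reactions of the withdrawal cases should be analyzed by a full data set". Its list of causes includes "lack of efficacy (deterioration or complications), violation of research programs".

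**Failure.** Section 4.8.1 item 4 says that subjects whose worsening angina needs other or more angina medicine "were withdrawn as invalid cases". *Invalid* is one of the outcome categories of the primary endpoint in section 8.1.1. Item 1 of the same list also concerns worsening, in subjects who "must take emergency treatment measures such as adjusting treatment drugs, hospitalization or surgery", but gives no outcome label.

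**PPS only.** Section 7.1.2 counts subjects who quit for aggravation as non-curative, but names only the PPS and only a duration of more than 4 weeks.

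**Main set.** Section 10.2.3(2) makes the FAS the main efficacy set. The primary time point is 12 weeks (10.2.3(10)).

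**Single measurements.** Section 10.2.1(3) ends with a garbled clause: "the measurements were made only once, and the mean of all the data was used to fill in the missing data". Section 4.8.3 lists absence of any record after dosing as a ground for excluding a case, without naming an analysis set.

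**The concern.** The primary endpoint is a category of change in the angina score, so each subject's code counts directly in the effective rate. For a subject who responds early and then leaves because angina worsens, carry-forward can keep the early success, while the *invalid* rule records a failure. These are the withdrawals in which the last recorded score is most likely to misstate the outcome. If the clauses are applied differently, the same data give different primary effective rates. The same subject could also be a failure in the PPS and a responder in the FAS, although the PPS is defined as a subset of the FAS.

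The single-measurement clause raises a smaller question. If it means subjects with a baseline score only, a mean fill could make a subject with no score after dosing *effective*.

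**Working it through.** **1. The rules applied to one subject.** Take a hypothetical subject scored by section 4.3.
- Baseline: frequency 4, duration 2, pain 2, nitroglycerin 2; total 10.
- Week 4: 2 + 1 + 1 + 1 = 5, a reduction of (10 − 5)/10 = 50%. This lies between the 30% and 70% cut points of 8.1.1, so the subject is *effective*.
- Week 6: withdrawn because worsening angina needs more angina medicine.

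| Clause | Set named | Code at week 12 |
|---|---|---|
| 10.2.1(3) carry-forward | none | *effective* |
| 4.8.2 carry-forward | full data set | *effective* |
| 4.8.1 item 4 | none | *invalid* |
| 4.8.1 item 1, if that is the ground | none | no label |
| 7.1.2 (more than 4 weeks) | PPS | failure |

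No section ranks these for the FAS. The visit schedule in 6.4 lists visits at −14 days, day 0 and weeks 4, 8 and 12. It lists no early-withdrawal visit whose score would replace the week-4 value.

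**2. The plan's own figure.** Section 3.2 uses 67.5% and 84.3%:
[67.5 × 32.5 + 84.3 × 15.7] / (84.3 − 67.5)² = 3517.26 / 282.24 = 12.462. Multiplied by the tabulated f = 7.9 this gives 98.45, against the stated 98.4 per arm. The sample size reproduces and does not depend on the coding rule.

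**3. Size per subject.** With 120 per arm, one recoded subject moves an arm by 1/120 = 0.83 points.

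**4. Bounds on the comparison.** The planned rates give 0.843 × 120 ≈ 101 test and 0.675 × 120 = 81 control responders. The check uses z = (difference in proportions) / √[p̄(1 − p̄) × 2/120], with p̄ the pooled rate and no centre adjustment. For 101 v 81, p̄ = 182/240 = 0.758 and z = 0.1667/0.0553 = 3.02. The protocol does not give the numbers recoded from *effective* to *invalid*; they are assumptions.

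| Recoded, test / control | Responders | Difference (points) | Two-sided p |
|---|---|---|---|
| 0 / 0 | 101 v 81 | 16.7 | 0.0026 |
| 7 / 7 | 94 v 74 | 16.7 | 0.005 |
| 7 / 4 | 94 v 77 | 14.2 | 0.015 |
| 7 / 0 | 94 v 81 | 10.8 | 0.059 (one-sided 0.0295) |
| 0 / 7 | 101 v 74 | 22.5 | 0.0001 |

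**5. Mean fill.** The clause does not say which mean, so the share of filled subjects coded *effective* is assumed to lie between 44% and 100%. The null simulation used 400,000 runs, a true rate of 67.5% in both arms, and loss unrelated to outcome. It counts z > 1.96 favouring the test arm (nominal 2.5%).

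| Handling of subjects with no post-dose score | Loss 5% test, 2% control | Loss 2% test, 5% control |
|---|---|---|
| Mean fill, share 44% to 100% | 1.9% to 3.6% | 3.3% to 1.7% |
| All coded *invalid* | 1.1% | 5.2% |
| Excluded | 2.5% | 2.5% |

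**The case against.** The best defence is that the clauses can be read together. Section 10.2.1(3) applies only when primary data are missing. If 4.8.1 item 4 already assigns *invalid*, nothing is missing. Section 4.8.2 stands under spontaneous withdrawal, and its list of causes is there to be recorded on forms. Section 7.1.2 can be read as keeping worsening withdrawals in the PPS as failures, which points the same way. A score recorded on leaving would also reflect the worsening and might bring the rules together.

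Much of this stands: 4.8.1 and 7.1.2 do lean towards failure. But 4.8.2 is worded to cover any cause and refers these cases to the full data set. Item 1 of 4.8.1 carries no label, and no withdrawal visit is scheduled. An analysis plan could set the order, but the protocol's clauses would still disagree.

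Three stronger readings are tempting but unsupported.
- *The coding could be steered by arm.* The blind audit (5.6(8)) receives the list of dropped subjects and makes decisions before lock. The first unblinding gives group codes only. The post-lock corrections in section 9(3) concern database problems and must be confirmed and recorded.
- *The conflict overturns the planned result.* Among the splits in the table, two-sided significance is lost only at 7 v 0, which nothing in the protocol supports. Even there the one-sided p is 0.0295, and 10.2.3(3) exempts the primary superiority test from the two-sided rule.
- *The mean fill seriously inflates error.* The sentence is garbled, baseline-only is an interpretation, and few subjects reach the fill if 4.8.3 is applied first.

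**Conclusion.** The point holds as an unresolved contradiction in the coding of the primary outcome in the FAS, limited to subjects who improve, then withdraw for worsening angina, with no later score recorded. The failure reading is the more natural one, but it is not stated for the FAS. Each such subject is worth 0.83 points in one arm. The direction is not predictable, and equal numbers in both arms leave the difference at 16.7 points. The figures are bounds that rest on the planned rates, 120 analysed per arm and assumed counts.

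The mean fill is a secondary point held with lower confidence. Its effect is small at modest loss and can run either way. The point is worth fixing because the remedy is a sentence and the result at stake is the primary one.

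**What to change.** Reconcile 4.8.1, 4.8.2, 7.1.2 and 10.2.1(3) as analysis coding only, with no change to any treatment or withdrawal rule. Settle this no later than the blind audit and before the first unblinding.

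1. State that a subject withdrawn for worsening angina or lack of efficacy is coded *invalid* in both FAS and PPS, at any week, ahead of carry-forward. This covers 4.8.1 items 1 and 4, and that cause under 4.8.2. It does not cover 4.8.1 items 2 and 3 (complications or physiological changes, and prohibited drugs).
2. Delete the mean fill. Reconcile 4.8.3 with 10.2.1(3) for subjects with no score after dosing, and report the result both with them excluded and with them coded *invalid*. Both are needed: exclusion holds the nominal error only if loss is unrelated to outcome, and *invalid* coding favours the arm with less loss.

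The cost is wording, one extra sensitivity analysis and slightly lower effective rates. As an illustration, recoding 6 subjects in each arm gives 79.2% v 62.5%, with the difference still 16.7 points and p = 0.005.

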10.2.2 Statistical expression

(1) The report is mainly expressed in tables, which are self-evident, i.e. with headings, annotations and examples.

(2) The results of repeated measurements can be expressed in tables or statistical charts to increase readability.

(3) Bilateral tests are used in statistical tests. Those whose P is less than or equal to 0.05 will be considered as having statistical significance.

10.2.3 Statistical analysis content

(1) CDAS3.0 statistical software will be used for statistical analysis.

(2) The main therapeutic data set was FAS analysis population, and the therapeutic PPS population was also analyzed.

(3) Except for the superiority test of the main therapeutic indicators, all other statistical tests are carried out by bilateral test, and the difference of P value less than or equal to 0.05 will be considered statistically significant.

(4) The measurements of each visit in different treatment groups will be described by means of standard deviation. Compared with the baseline values at the time of admission, paired t-test was used to compare the differences between before and after admission. Variance analysis was used to compare the changes before and after treatment in each group.

(5) Frequency (constituent ratio) was used to describe the counting data of each visit in different treatment groups. 2 test or non-parametric test were used to test the changes before and after treatment in each group.

(6) Comparability analysis: Comparing demographic data and other basic value indicators to measure the comparability between the two groups.

(7) Compliance analysis: Compare the two groups of patients whether to use the research drugs on time and in quantity, not using the drugs prohibited in the program.

(8) Abscission analysis: χ^2 test will be used to compare the total abscission rate and the abscission rate due to adverse events in each group.

(9) Equilibrium analysis of basic values: using variance analysis or 2 test to compare demographic data and other basic value indicators to measure the two groups of equilibrium.

(10) Effectiveness analysis: PPS and FAS were used to analyze the main indicators and global indicators, and CMH test considering the central effect was used to analyze the efficacy of the two groups. The main effect indicators were selected to treat 12 weeks of angina symptoms, and the placebo was used as the control for statistical test.

(11) Analysis of factors affecting efficacy: If there are significant correlative factors affecting efficacy, these factors should be considered as covariance analysis or logistic regression analysis when comparing the efficacy of the two groups. Detailed list of combined medication is required.

(12) Safety analysis: 2 test was used to compare the incidence of adverse events in the two groups, and list the adverse events in the study; analysis of the normal/abnormal changes of laboratory results before and after the study and the relationship between abnormal changes and research drugs.

11. Quality Control and Guarantee of Clinical Trials

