3.2 Sample size

According to the statistical requirements, the sample size was estimated. The main effect index was the curative effect of angina pectoris symptoms treated for 12 weeks. According to the literature, the total effective rate of basic treatment plus placebo was 67.5%, and the

total effective rate of basic treatment plus experimental drugs was predicted to be 84.3%. Set $\alpha=0.05$, $1-\beta=0.2$, According to the experimental group: control group = 1:1 set up group,

$$n = \frac{P_1 \times (100 - P_1) + P_2 \times (100 - P_2)}{(P_2 - P_1)^2} \times f(a, b)$$

The minimum sample size to meet the statistical requirements was 98.4 cases in each group, and the dropping rate was not more than 20%, 120 cases in each group, a total of 240 cases.

4. Subject selection and withdrawal

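### The protocol contradicts itself on whether the primary superiority test is one- or two-sided, and the only significance level it states is 0.05

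*Protocol*

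**What the plan says.** Two clauses of the protocol, both in section 10.2, govern the side of the tests.

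- Section 10.2.2(3), the general rule: "Bilateral tests are used in statistical tests". The threshold follows: "Those whose P is less than or equal to 0.05 will be considered as having statistical significance". No test is excepted.
- Section 10.2.3(3): "Except for the superiority test of the main therapeutic indicators, all other statistical tests are carried out by bilateral test", and for these other tests "the difference of P value less than or equal to 0.05 will be considered statistically significant". The primary test is left out of the two-sided rule. No side and no level is written for it.

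Section 10.2.3(10) names the primary method, "CMH test considering the central effect was used to analyze the efficacy of the two groups", for the 12-week angina symptom effect, again without a side or level.

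Section 3.2 sets alpha at 0.05 without a side. It assumes effective rates of 67.5% (placebo) and 84.3% (capsule) and arrives at "98.4 cases in each group", raised to 120 for dropout. The abstract repeats this. A level of 0.025 appears nowhere in the protocol.

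**The concern.** A test that is excepted from two-sided testing is naturally read as one-sided. The only level available to it is 0.05, so the protocol supports two different success criteria for its main efficacy comparison: two-sided P ≤ 0.05 under 10.2.2(3), or one-sided P ≤ 0.05 under 10.2.3(3).

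These are not equivalent. In the capsule's favour, the first carries a 2.5% false-positive rate and the second 5%. A result can meet one and miss the other. While both clauses stand, the protocol does not fix the criterion before the data are seen, and an analyst could cite either clause in support of the choice.

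**Working it through.** **Inputs (protocol section 3.2).** Placebo rate 67.5%, capsule rate 84.3%, alpha 0.05, 1:1 allocation, 120 per group enrolled, up to 20% dropout. The printed power statement gives 0.2 for 1−β. It is read here as β = 0.2, or 80% power, because the stated size reproduces only that way.

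**Step 1: reproduce the stated size.** The protocol's formula is n = [P1(100−P1) + P2(100−P2)] / (P2−P1)² × f, with f = (z_α + z_β)².

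- Numerator: 67.5 × 32.5 + 84.3 × 15.7 = 2193.75 + 1323.51 = 3517.26
- Denominator: 16.8² = 282.24
- Ratio: 3517.26 / 282.24 = 12.46

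| Test at 80% power | f | n per group |
|---|---|---|
| Two-sided 0.05 (same as one-sided 0.025) | 7.849 | 97.8 |
| The same, f rounded to 7.9 | 7.9 | 98.4 |
| One-sided 0.05 | 6.183 | 77.0 |

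Working backwards, 98.4 implies f = 7.896. The trial was therefore sized for two-sided 0.05 or its one-sided 0.025 equivalent, not for one-sided 0.05.

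**Step 2: false-positive rate in the capsule's favour.** A two-sided 0.05 test puts 2.5% in the favourable tail and a one-sided 0.05 test puts 5% there. The rate doubles.

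**Step 3: results that split the clauses.** This uses a pooled two-proportion z test, 120 per group, with 81/120 responders on placebo (67.5%).

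| Capsule responders | Difference (points) | z | One-sided P | Two-sided P | Outcome |
|---|---|---|---|---|---|
| 92 | 9.2 | 1.583 | 0.057 | 0.113 | fails both |
| 93 | 10.0 | 1.735 | 0.041 | 0.083 | split |
| 94 | 10.8 | 1.888 | 0.029 | 0.059 | split |
| 95 | 11.7 | 2.044 | 0.020 | 0.041 | passes both |

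**Step 4: width of the split zone.** The smallest significant difference is z × √[p(1−p) × 2/120], where p is the pooled rate.

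- p = 0.76, about the midpoint of the planned rates: standard error 5.51 points, so 1.645 × 5.51 = 9.1 points one-sided and 1.960 × 5.51 = 10.8 points two-sided.
- p = 0.725, which fits a 10-point difference over a 67.5% placebo rate: standard error 5.76 points, so 9.5 and 11.3 points.

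**Step 5: power and chance of a split at the planned rates.**

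| Per group | Power, two-sided 0.05 | Power, one-sided 0.05 | Gap |
|---|---|---|---|
| 120 | 86.5% | 92.3% | 5.8 points |
| 96 (20% lost) | 78.1% | 86.4% | 8.3 points |

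The gap is the probability that the result meets the one-sided criterion but not the two-sided one.

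**The case against.** The strongest reply is that one-sided at 0.05 takes two inferences. Section 10.2.3(3) never uses the words one-sided, and its 0.05 threshold grammatically belongs to the other tests. Read together with the sample size, the exempted test could be meant at one-sided 0.025. In the capsule's favour that is the same criterion as two-sided 0.05: nothing doubles and no result splits. The usual CMH chi-square statistic is also non-directional, which fits the two-sided reading. An SAP, not available here, may settle the matter.

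Part of this stands. The doubling and the split are conditional on the one-sided 0.05 reading. The width of the split zone depends on the pooled rate: 92 capsule responders, a 9.2-point difference, would lie inside the 9.1 to 10.8 band calculated at 76%, yet fail both tests when placebo is at 67.5%. The planned 16.8-point effect would clear either threshold.

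The contradiction is untouched. The protocol does not state 0.025, so the harmless reading has to be supplied by the reader. If the exception does not mean one-sided at 0.05, the protocol gives its primary test neither a side nor a level under 10.2.3(3). Naming the CMH test fixes neither. An SAP can follow 10.2.2(3) or the exception in 10.2.3(3) but not both, so this is a conflict in the protocol and not a detail left for later.

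**Conclusion.** The concern holds. Sections 10.2.2(3) and 10.2.3(3) give incompatible rules for the primary test, and only the first agrees with the sample size in section 3.2.

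If the exemption is taken as one-sided at the only stated level, the false-positive rate in the capsule's favour is 5% against 2.5%. Observed differences of roughly 9 to 11 points at 120 per group then succeed under one clause and fail under the other. At the planned rates the chance of such a result is about 6% with 120 per group and about 8% with 96. If one-sided 0.025 was intended, there is no numerical harm, but the protocol does not say so.

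The figures rest on an unstratified two-proportion z test. The planned centre-stratified CMH test will shift the exact cut-offs, not the conflict. Because the defect lies in the success criterion of the main comparison, it must be fixed.

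**What to change.** Delete the exception in section 10.2.3(3). State that the centre-stratified CMH test of the 12-week angina effective rate is two-sided at 0.05 (equivalently one-sided 0.025), reported with a two-sided 95% confidence interval for the difference in rates. Add the word two-sided to alpha in section 3.2 and the abstract, so that the 98.4 calculation and the test visibly match.

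Keeping the exception and printing a one-sided level of 0.025 would give the same criterion for a claim in the capsule's favour, but section 10.2.2(3) would then need a matching exception.

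The cost is essentially one sentence. No more patients are needed, because 120 per group already rests on a two-sided 0.05 test. The sponsor gives up only the laxer reading, for which the trial was not sized.

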6.2.2 Effectiveness indicators

Main effective indicators: the efficacy of angina symptoms.

Secondary effectiveness indicators:

- (1) Curative effect of TCM syndromes;
- (2) Grading changes of severity of angina pectoris;
- (3) Changes in the number of angina attacks per week;
- (4) Nitroglycerin dosage;
- (5) Seattle Angina Scale score;
- (6) Blood HCY: The changes of blood HCY before and after treatment were compared between the two groups.
- (7) Incidence of cardiovascular events (sudden cardiac death, acute myocardial infarction, heart failure, percutaneous transluminal coronary angioplasty, coronary artery bypass grafting, malignant arrhythmia, cardiogenic cerebrovascular accident, angina pectoris requiring hospitalization, etc.).

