6.2.4 Other observational indicators

- (1) Fasting blood glucose: The changes of fasting blood glucose before and after treatment were compared between the two groups.
- (2) Four items of blood lipid: The changes of four items of blood lipid before and after treatment were compared between the two groups.

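### Free improvement: change scores of continuous outcomes are compared by analysis of variance with no baseline term, where ANCOVA would be more precise at no cost

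*Protocol*

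**What the plan says.** Protocol section 10.2.3 item (4) sets out the analysis of measurement data. Each arm is compared with its own baseline: "paired t-test was used to compare the differences between before and after admission". Then: "Variance analysis was used to compare the changes before and after treatment in each group". No baseline covariate and no other model term is named.

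The outcomes that this reaches are described elsewhere as between-arm comparisons of change:

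- HCY, section 6.2.2 item (6): "The changes of blood HCY before and after treatment were compared between the two groups".
- SAQ, section 8.1.2 item 5): "Compare the changes of each dimension of the Seattle Angina Scale before and after the treatment of the two groups".
- Fasting glucose, section 6.2.4 item (1), with a parallel entry for the four lipids: "The changes of fasting blood glucose before and after treatment were compared between the two groups".

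The baseline values exist. Section 6.4.2 (Visit 2, before treatment) collects the SAQ, HCY, fasting glucose and lipids, and Visit 5 (week 12) repeats them. Section 5.4 states that randomisation is done by centre.

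Three other provisions limit the scope. Section 10.2.1 item (1) lets the method change, or the data be transformed, when data are not normal. Section 10.2.3 item (5) gives counting data a different treatment: "test or non-parametric test were used to test the changes before and after treatment in each group". Item (10) gives the primary outcome its own centre-adjusted test: "CMH test considering the central effect was used to analyze the efficacy of the two groups".

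**The concern.** Item (4) already assigns the within-arm comparison to the paired t-test. The analysis of variance of changes is then left as the test between arms, although the phrase about each group is awkward in translation. An analysis of change scores subtracts the whole baseline value. ANCOVA subtracts only the part of it that predicts the outcome, so its residual variance is smaller or, at the limit, equal. Patients and measurements are the same in both.

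What is at stake is precision for the SAQ dimensions and HCY: wider confidence intervals and lower power than the collected data allow. Neither the validity of the comparison nor the primary conclusion is at stake.

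**Working it through.** **The plan's own figure.** Section 3.2 gives 98.4 per group, from response rates of 67.5% and 84.3%. Its formula gives [67.5 × 32.5 + 84.3 × 15.7] / 16.8² × f = 3517.26 / 282.24 × f = 12.462 × f. With f = 7.9 (rounded, two-sided 5%, 80% power) this is 98.45; with f = 7.849 it is 97.81. So the stated figure reproduces, provided that the printed power term of 0.2 is read as β. It rests only on the binary primary outcome, so item (4) plays no part in it. The protocol gives no power calculation for any continuous outcome.

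**Inputs for the comparison.** There are 120 patients per arm and up to 20% dropout (section 3.2), which leaves 120 × 0.8 = 96 per arm. The test is two-sided at 5% (section 10.2.2). Power of 80% is used, giving 1.960 + 0.842 = 2.802. The baseline-to-week-12 correlation r and the ratio k of the week-12 SD to the baseline SD are not in the protocol. Both are assumed over a range.

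**Variances**, in units of the squared baseline SD:

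- Change score: 1 + k² − 2rk.
- ANCOVA: k²(1 − r²).
- Difference: (1 − rk)². This is never negative, so ANCOVA is never the less precise of the two in large samples. They are equal only when rk = 1.

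**Equal SDs (k = 1).** The variance ratio is (1 − r²) / [2(1 − r)] = (1 + r)/2. The detectable difference in SD units is 2.802 × √(2/96) = 0.404, multiplied by √[2(1 − r)] for change scores or by √(1 − r²) for ANCOVA.

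| Assumed r | Variance ratio | Detectable, change score | Detectable, ANCOVA |
|---|---|---|---|
| 0.3 | 0.65 | 0.478 | 0.386 |
| 0.5 | 0.75 | 0.404 | 0.350 |
| 0.7 | 0.85 | 0.313 | 0.289 |
| 0.9 | 0.95 | 0.181 | 0.176 |

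In terms of power: where the change-score analysis has 80% with 96 per arm, ANCOVA has about 93.5% at r = 0.3, 89.9% at 0.5, 86.0% at 0.7 and 84.0% at 0.8.

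**Unequal SDs**, for r = 0.3, 0.5, 0.7 and 0.9:

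- k = 0.75: ratios 0.46, 0.52, 0.56, 0.50.
- k = 1.25: ratios 0.78, 0.89, 0.98, 0.95.

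Over all these assumptions the ratio runs from 0.46 to 0.98, that is, from about half the variance to almost no change.

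**The case against.** The strongest reply is that a valid method is being exchanged for a preferred one, and that model terms for secondary outcomes belong in a statistical analysis plan. Section 9 item (4) refers to such a plan. Much of this stands. Change-score analysis is unbiased here, the size of the gain rests wholly on r and k, and a plan that is not shown may already specify ANCOVA. But item (4) does not leave the method open: it names a change-score analysis, and a better use of the same data can be suggested against that.

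Adjustment is also not excluded. Item (11) says: "If there are significant correlative factors affecting efficacy, these factors should be considered as covariance analysis or logistic regression analysis". That stands too, but the route is conditional on observed significance and does not name the baseline value.

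Three stronger readings are tempting, and the document does not support them.

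- A reader might infer that leaving out centre also costs precision. No such loss can be shown. Item (4) lists no terms at all, which does not bar centre as a factor, and a change score already cancels a constant centre shift.
- A reader might infer that items (10) and (11) leave the primary test undecided and so inflate type I error. Item (10) assigns the CMH test to the 12-week primary outcome, and the rank of a supportive model is ordinary analysis-plan content. Error would rise only if someone chose the smaller p-value after seeing both results, which no passage permits.
- A reader might extend the point to every secondary outcome. It does not reach CCS grade or the cardiovascular event rate. It reaches weekly attacks, TCM score and nitroglycerin use only where they are analysed as continuous. Glucose and lipids are not listed among the efficacy indicators and are also safety laboratory items, so precision matters less there.

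**Conclusion.** The point holds as an optional improvement, not as an error. For outcomes analysed as continuous, the stated analysis is valid but uses the baseline data less efficiently than ANCOVA. With equal SDs, ANCOVA has 5% to 35% less variance for r from 0.9 down to 0.3: a clear gain at low correlation and almost none at high correlation. The conclusion rests on reading the analysis of variance in item (4) as the between-arm comparison, on assumed values of r and k, and on large-sample variance formulas. That ANCOVA is at least as precise does not depend on the assumed r and k; how much is gained does. The primary CMH test and the planned 240 patients are unaffected.

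**What to change.** In section 10.2.3 item (4), state that between-arm comparisons of outcomes analysed as continuous, chiefly the SAQ dimensions and HCY, use ANCOVA of the week-12 value (or the change) on treatment, baseline value and centre. Keep the section 10.2.1 item (1) provision for non-normal data. Centre is included because randomisation is by centre. The paired t-tests can stay as within-arm description.

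The cost is a change of analysis wording only. Baseline values and centre codes are already recorded, and no patient, visit or procedure is added. If the statistical analysis plan already specifies this model, the protocol sentence need only be aligned with it.
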